2.1 Evaluation of operational characteristics (invalid and indeterminate rates) of Typhoid RDTs

Primary Endpoint:

- 1.1 Point estimates of sensitivity and specificity for each test, with 95% confidence interval, using blood culture as reference standard.\
- 1.2 Establishment of a biorepository of well characterized specimen collection at the site available for future assessments of emerging technologies

Secondary Endpoints:

2.1 Estimates of operational characteristics of different RDTs based on quantitative assessment including invalid and indeterminate rates

DESIGNS AND METHODOLOGY

Trial Site

The study will take place in three hospitals in Nairobi County, found in Sub-Saharan Africa (Kenya). The three hospitals in Nairobi are Mbagathi County Hospital, [name]; Medical Missionaries of Mary, Reuben Centre Hospital in Mukuru Slum, Embakasi and City Council Clinic in Mukuru Slum, Embakasi.

Justification for selectig the the three study hospitals: Mbagathi County Hospital, [name] draws majority of its patients from Kibera informal settlement (slum), an area with high burden of bacterial infections due to poor sanitation and limited resources. Kibera is a large, densely populated (77,000 persons/km²) urban settlement situated within Nairobi, a city with >4 million inhabitants. It is characterized by poor sanitation evidenced by excreta and garbage in footpaths and open sewers. Water supply in Kibera is largely unregulated and food vendors trade outdoors under minimal hygiene standards (Njuguna, 2013).

Medical Missionaries of Mary, Reuben Centre Hospital and City Council Clinic are located with andserves Mukuru informal settlement (slum) population. Maukuru slum also suffers from high bacterial disease burden due to poor sanitation and limited resources. Mukuru slum (20 km East of Nairobi) is home to a population of over 150,000 in an area approximately 2km²(population density, 75,000/km²) [Kenya Population Census, 2010] living in congested housing and under poor sanitary conditions. The majority of the populations work in nearby industrial areas.

Study Design

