All samples preparations (blood culture and serum preparation) will be conducted in parallel. Blood culture will be done using an automated blood culture system (BD BACTEC 9050). BACTEC vials will be processed as per manufacturer's instructions. Bottles will be incubated until signal-positive or till the end of day 5, whichever is earlier. When positive signal is observed, bottles are unloaded from instrument and Gram's stain and cultures and biochemical tests to identify *Salmonella* Typhi will be performed using standard microbiological procedures. Patients will be classified as typhoid or non-typhoid cases according to the blood culture results. However, since the results of the blood culture may take several days to be available, serum will be separated from all whole blood samples and will be aliquoted. It is expected that at least 100 blood culture positive and 100 blood culture negative samples will be tested with index tests and will be kept for long term storage.

Testing with the index tests will be performed in batch at the end of each month while the remaining volumes of the selected sera will be kept at -80°C. Depending on the initial volume that will differ between adult and children samples, 3 to 6 aliquots will be kept at -80°C for long term storage and will be used for future evaluation of diagnostic tests.

Investigational products

Reference standard tests to identify Salmonella Typhi:

All blood samples collected from study participants will undergo blood culture.

• Blood culture: Blood culture is considered as gold standard for the diagnosis of typhoid fever. Blood culture is a routine process for diagnosis of typhoid fever.

Index tests:

Index tests are RDTs that will be performed according to manufacturer's instructions by trained laboratory personnel. The readers of the index tests and reference standard test will be blinded to the results of the other tests.

Typhoid RDTs for inclusion in the study were selected by the study team based on a combination of the following criteria:

- RDT is CE-marked
- Published independent evaluation data
- International availability
- Volume of samples
- Price of the test
- Turnaround time

RDTs will be procured by FIND and shipped to the study sites in Kenya. There are no financial ties of any nature with the manufacutrers. All selected RDTs which will be included in the study are shown in Table 2.

Table: 2 Lists of RDTs

1	SD Bioline Salmonella Typhi IgG/IgM Fast

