The statistical analysis plan (SAP) will be developed and finalized before the start of enrolment and will describe in detail the methodology used to evaluate each of the endpoints. This section is a summary of the planned statistical analyses of the primary and secondary endpoints.

Endpoint	Statistical Analysis Methods
1.1	Point estimates of sensitivity and specificity for each test with 95% confidence interval, using Blood culture as reference standard.
1.2	Establish a biorepository of well characterized specimen collection that can be used to evaluate emerging tests.
2.2	Evaluation of operational characteristics of different RDTs including invalid and indeterminate rates.

- Efficacy Analyses

Analysis datasets

The following datasets will be defined:

- ITT (Intention-To-Test) all subjects successfully enrolled in the study
- MITT (Modified-Intention-To-Test) all subjects in ITT for whom at least one test result is available
- PP (Per-Protocol) all subjects in ITT for whom results for all tests are available (complying with the protocol)

Description of statistical methods

General approach

Estimates of accuracy

Table 5 summarizes the way results of diagnostic tests are reported when two tests are compared. Based on the definitions in the table, the following values are defined:

Sensitivity = TP / (TP + FN)

Specificity = TN / (FP + TN)

For each point estimate, a 95% confidence interval will be derived based on the Wilson's score method. Missing and invalid results (e.g. the results for one specific test for a given participant) will not be imputed and will be removed from the analysis.

Table 5 Definition of test results

	Reference Standard Outcome								
t		Reference positive	Reference negative	Total					
result	Test result Positive	ТР	FP	PP = TP + FP					
Test	Test result negative	FN	TN	PN = FN + TN					
	Total	P = TP + FN	N = FP + TN	P + N					

TP = true positives, TN = true negatives, FP = false positives, FN = false negatives, P = positive, N = negative

Analysis of the primary outcome(s)

Outcome 1.1

This outcome will be evaluated with the methodology described in section 4.1.1, using using blood culture as reference standard, on the PP population, for each test included in the trial. Outcome 1.2

This outcome does not require any statistical analysis.

Analysis of the secondary outcome(s)

Outcome 2.1

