The number of indeterminate and invalid test results will be reported for each RDT, together with the relative percentage over the total number of tests performed.

Baseline descriptive statistics

Descriptive statistics tables will be generated to summarize the characteristics of the participants in the PP and ITT populations, per.

The number of participants included and excluded will be reported, overall and for each clinical site and test. Among the included samples, the information will be broken down by the following variables:

Socio-demographics:

Age (<11, 12:17, >17)
Gender (female, male)
Clinical site
Sample characterization:
Reference test positive or negative
Results will be reported either in absolute numbers (e.g. number of subjects in a group) or summarized by mean, median, standard deviation, minimum, maximum and quartiles.

Details on the methodology will be provided in the SAP.

QUALITY MANAGEMENT

Quality Management for this trial consists of Quality Control activities, training and capacity building, as well as the use of Standard Operating Procedures, Work Instructions, Tools and Templates.

Training on the protocol, GCP and the use of the IVDs and laboratory tests will be provided by the study team. A Laboratory Manual, which describes all of the sample testing procedures, will be provided by the study team prior to the commencement of the Trial. Training on the EDC system will be provided by FIND Data Management prior to first participant enrolment.

Quality control (study monitoring)

Quality control will be applied to each stage of data handling to ensure that all data are reliable and have been processed correctly. The study team will perform risk based monitoring of this trial, and associated Quality Control checks, as described in the Monitoring Plan. Independent trial monitors will perform source data review and source data verification to confirm that data entered into the CRF by authorized site personnel are accurate, complete, and verifiable from source documents; that the safety and rights of participants are being protected; and that the trial is being conducted in accordance with the currently approved protocol and any other trial agreements, ICH GCP, and all applicable regulatory requirements.

Quality Assurance (auditing)

As part of routine Quality Assurance, the study team will conduct an audit of the study sites.

Trial site closure

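### Endpoint 2.1 promises an indeterminate rate for each RDT, but no result field on the RDT form codes it and the term is not defined

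*Combined protocol and SAP*

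**What the plan says.** Four places commit to the indeterminate rate.

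- Secondary Objectives, 2.1: "Evaluation of operational characteristics (invalid and indeterminate rates) of Typhoid RDTs".
- Secondary Endpoints, 2.1: "Estimates of operational characteristics of different RDTs based on quantitative assessment including invalid and indeterminate rates".
- Endpoint table in the Statistical Analysis Plan section, where the row is numbered 2.2: "Evaluation of operational characteristics of different RDTs including invalid and indeterminate rates".
- Analysis of the secondary outcome(s), Outcome 2.1: "The number of indeterminate and invalid test results will be reported for each RDT", each as a percentage of all tests performed.

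On conduct, the Index tests section states: "Index tests are RDTs that will be performed according to manufacturer's instructions by trained laboratory personnel". The notes to Table 2 add that the package inserts are available.

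On analysis, the Estimates of accuracy section covers two kinds of unusable result: "Missing and invalid results (e.g. the results for one specific test for a given participant) will not be imputed", and these are removed. It has no rule for indeterminate results. The primary accuracy analysis uses the per-protocol (PP) set, which is limited to enrolled subjects with a result on every test.

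On data capture, the RDT form in Appendix 1 gives each readout an initial field and a repeat field. Both offer Pos, Neg and Inv, and the repeat is for invalid results. There is a Comments column beside the results. The only instruction about comments on that form is to explain an RDT that was not done. The Source Data section says that the paper CRF mirrors the electronic one, and Table 3 makes the lab notebook or LIMS the original record of laboratory results.

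**The concern.** A rate can be reported only if the event is defined and recorded. Here the invalid rate has a field and the indeterminate rate does not. Following the form exactly gives an invalid count for every RDT and no indeterminate count for any. The analyst could not tell a true zero from reads that nobody was asked to record.

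There is also a conditional effect. If a package insert recognises an equivocal read, the person completing the form must enter it as Pos, Neg or Inv. Entered as Pos or Neg, it goes into sensitivity or specificity unmarked, because only missing and invalid results are removed. Entered as Inv, it adds to the other rate in endpoint 2.1 and prompts a repeat. Two readers could choose differently and the coded data would not show it.

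**Working it through.** The plan states no figure for this rate, so there is none to reproduce. The check is a count of the form's fields against the endpoint.

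**Step 1. Result fields on the RDT form (Appendix 1).** Fields = readouts × 2, one initial and one repeat. The SD Bioline rows are scrambled in the extracted text, and I counted that test as one IgG and one IgM line.

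| Type of test | Tests | Readouts per test | Fields |
|---|---|---|---|
| Single result: Widal, TUBEX TF, Enterocheck WB, Test-it, S. typhi/S. paratyphi A direct antigen, Diaquick antigen | 6 | 1 | 6 × 1 × 2 = 12 |
| IgG and IgM: Typhidot, SD Bioline, Combo Rapid Test, Rapid Test Cassette, Diaquick antibody | 5 | 2 | 5 × 2 × 2 = 20 |
| Total | 11 | | 12 + 20 = 32 |

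The 32 fields are 16 initial and 16 repeat. Fields that offer an indeterminate code: **0 of 32**. Fields that offer an invalid code: 32 of 32.

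**Step 2. Other routes in the document.**

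| Route | What it provides | Enough for a rate? |
|---|---|---|
| Repeat row | A second read after an invalid result | No, an indeterminate read does not trigger it |
| Comments | Free text, with an instruction only for tests not done | No, recording is not requested |
| eCRF | Same design as the paper form | No separate code is indicated |
| Lab notebook or LIMS | Original record of laboratory results | Possibly, but nothing asks for equivocal reads |
| Definition of the term | None; it appears only in the objective, the endpoint, the endpoint table and the outcome 2.1 text | No |

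**Step 3. What a coded rate would give.** The Study workflow section expects at least 100 culture-positive and 100 culture-negative sera, so n = 100 + 100 = 200 per RDT. The plan asks only for a count and a percentage here. I add Wilson 95% limits, the method it uses for accuracy, with z² = 3.84.

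- True count 0 of 200: upper limit = z²/(n + z²) = 3.84/203.84 = 1.9%.
- Assumed count 10 of 200: centre = (0.05 + 3.84/400)/(1 + 3.84/200) = 0.0585; half-width = 1.96 × √(0.05 × 0.95/200 + 3.84/(4 × 200²))/(1 + 3.84/200) = 0.0311. The rate is 5.0% (2.7% to 9.0%).

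The sample is therefore large enough to give a useful rate; the obstacle is the missing code. A blank on the present form does not support the 1.9% bound, because it does not show that indeterminate reads were looked for.

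**Step 4. Counting unit.** The outcome text counts per RDT, but five tests yield two results per serum. For those tests the denominator could be 200 sera or 2 × 200 = 400 lines, before any repeats. The text does not say which.

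**The case against.** The strongest reply is that other documents may settle this. The Statistical Analysis Plan section is only a summary of a SAP that "will be developed and finalized before the start of enrolment". A Laboratory Manual is to describe the testing procedures, and a Data Management Plan covers the database. Any of these could define the term, and source records might allow reads to be recovered. That stands as a limit on the claim: the rate is unavailable from coded data, not proved unrecoverable. But a definition elsewhere does not add a field to the form, and the form must match it.

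Secondly, the tests may have no indeterminate category. The inserts are not reproduced, so this is open. If so, accuracy is unaffected and the only defect is a promised rate with no content, cured by deleting it.

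Thirdly, the outcome 2.1 sentence could mean one pooled count, which the Inv box would hold. The wording there permits this, but the objective and endpoint speak of rates in the plural and name both. If one category is meant, the text should say so.

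A reader might go further and infer that the primary sensitivity and specificity are biased, and try to size the bias by moving assumed equivocal reads between positive and negative. The document does not support that. It gives no frequency of such reads and does not show that any test has them. A read coded Inv goes to a repeat and may end with a valid result. If it does not, the PP requirement for results on every test may remove that participant from the analysis of all 11 tests, so even the denominator is not fixed.

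**Conclusion.** The mismatch holds. The plan commits in four places to an indeterminate rate, and 0 of 32 result fields on the supplied form can record one. The term has no definition in the document, and the repeat row does not cover it. One of the two rates named in the only secondary endpoint cannot be produced from coded data, and absence of a record cannot be reported as zero.

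This rests on the form in Appendix 1 being the one used and on the eCRF having the same codes, as the Source Data section indicates. The field count needs no other assumption.

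Any effect on accuracy or on the invalid rate depends on whether at least one test has an equivocal category, and its size is unknown. The point does not show that the primary analysis is wrong. It should be corrected before testing starts, because equivocal reads that nobody writes down in the monthly batches may not be recoverable later.

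**What to change.** Before the first batch is tested:

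1. From the package inserts, state for each of the 11 tests what counts as indeterminate, or that it does not apply.
2. Where it applies, add a coded option to the initial and repeat fields in the CRF and eCRF, and state whether such a read leads to a repeat.
3. Report it separately from invalid, and state whether the count is per test or per IgG/IgM line and whether repeats enter the denominator.
4. State in the SAP how such reads are handled in the accuracy analysis and in the PP set, consistently with the manufacturer's instructions. The document gives no basis for preferring one rule here, so the choice belongs to the study team, made in advance.

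If no test has the category, delete the indeterminate rate from objective 2.1, endpoint 2.1, the endpoint table and the outcome 2.1 text. If indeterminate and invalid are meant as one category, say so in the same places.

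The cost is one CRF and eCRF edit, a short definition table and brief reader training, or a text deletion only.

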Typhoid fever is an enteric bacterial infection caused by *Salmonella enterica* serovar Typhi (Salmonella Typhi; S. Typhi). It is an important infectious disease in low- and middle-income countries with over 10.9 million new cases worldwide and 116.8 thousand death in 2017. South Asia and Sub Saharan Africa are the most affected areas of the world. Typhoid fever is common in areas with inadequate sanitation and hyegine. In routine practice, diagnosis of typhoid fever is rarely confirmed as diagnostic tests are unavailable or have limited diagnostic accuracy. Blood culture is the commonest reference standard test but has a lower sensitivity. Alternatives to those methods exist but their performance is poor. The Widal test is still used but as it is based on cross-reactive antigens, it lacks sensitivity and specificity. Clinician often use rapid diagnostic tests to diagnose typhoid. A number of typhoid fever RDTs are commercially available but performance data are not available or not consistent from a study to another. This prospective, multicentre, cross-sectional study will be carried out in 3 hospitals of Nairobi, Kenya. 2000 clinically suspected typhoid cases will be enrolled in this study, blood culture as well as serum for RDT will be received. All typhoid positive and equal typhoid negative serum will be tested for investigational RDTs.

This collaborative study between KEMRI and FIND will systematically compare different point of care typhoid tests currently available in the market against the same set of reference standard. The knowledge gained from this trial may benefit health providers' by providing information on diagnostic accuracy of current typhoid test and to decide on utility of these commercial tests. The result obtained from this trial will also be made available to help inform Ministry of Health in Kenya and the WHO Essential Diagnostic list (EDL) and stakeholder decision making more broadly.

LAY SUMMARY

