This is a prospective multicentre diagnostic accuracy study using collected blood and/or serum samples that will be conducted in three hospitals at Nairobi, Kenya. Participants will be recruited when they present to three hospitals where the study will take place. Clinical officers appointed in the 3 hospitals will collect blood samples from individuals older than eight years presenting with fever because most documented typhoid fever cases involve school-aged children and young adults. The samples will be transported in cold chain to the Centre for Microbiology Research (CMR), KEMRI laboratories where they will be processed using blood culture. Once culture results are available, investigational RDTs will be performed on all blood culture positive and equal culture of negative serum.

Trial Population

The trial population will be composed of adults and children suspected of typhoid between 8-65 years of age because most documented typhoid fever cases involve school-aged children and young adults. Participants will be recruited in 3 hospitals in Nairobi, Kenya.

Inclusion Criteria

Participants are eligible to be included in the Trial only if all of the following inclusion criteria apply:

- Individuals aged 8 years of age to 65 years of age
- History of fever or axillary temperature of >37.5^oCfor at least 3 consecutive days within the last 7 days prior to enrolment
- Clinical suspicion of enteric fever
- One of the following scenarios:
 - Presents to outpatient department or Emergency Department
 - Admitted to hospital within last 12 hours
- Able and willing to provide informed consent (and assent when required)

Exclusion Criteria

Participants are excluded from the Trial if any of the following exclusion criteria apply:

- Unwillingness to participate in the study
- Inability to provide the required volume of blood
- Unwillingness to provide blood
- Known non-infectious / Non typhoid Infectious causes of fever or other alternate diagnosis of fever

Screen Failures

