The reported values for prevalence of Salmonella Typhi positive patients in Kenya is 5% (Data from personal communication with [name] Co-PI). The reported values of sensitivity and specificity of diagnostic tests are generally low, (Review article on typhoid RDTs summarizes TUBEX test from IDL Biotech has sensitivity of 78% and specificity of 87%, TestTM It from LifeAssay has sensitivity of 69% and specificity of 90%, Typhidot from Reszon Diagnostic has sensitivity of 78% and specificity of 77%.(9) Similarly reported sensitivity and specificity of SD Bioline Salmonella Typhi IgG/IgM from Abbot and Typhoid IgG/IgM Combo rapid test from CTK Biotech are 69%/76% and 40-79%/68-79% respectively (15)). For the purpose of determining the sample size, sensitivity and specificity were both assumed to be 50%, which corresponds to the scenario that requires the highest number of samples to estimate sensitivity and specificity. Based on this hypothesis, and on the feasibility of recruitment at the sites of enrolment, it was decided to set the sample size in order to recruit at least 100 culture positive and culture negative samples in Kenya. These sample sizes will allow to estimate the sensitivity of the test with 80% power to detect a 95% confidence interval of width of +/- 14% in Kenya (11). Based on the prevalence mentioned above, this number of positive samples requires the enrolment of at least 2,000 participants in Kenya (at a prevalence of 5%). From a similar study carried out by an MSc student in our lab that we supervised (Performance of tubex® tf IGM antibody test against culture in typhoid fever detection in Nairobi county, MSc Thesis by [name], JKUAT, 2019), the average number of patients presenting with febrile illnesses at Mbagathi County Hospital was 20 per day, using this as a basis and considering their relatively smaller sizes, we estimate that for Medical Missionaries of Mary, Reuben Centre Hospital and City Council Clinic, we will have 10 and 5 patients presenting per day in Medical Missionaries of Mary, Reuben Centre Hospital and City Council Clinic respectively. We plan to sample for only 3 days in a week (Mon-Wed) due to the observed trend of high patient inflow on these days from [name]

[name]'s MSc work (total 35 patients per day, 420 per month). This works out to a minimum of 2,520 which is above the sample size of 2,000 participants that we are targeting.

TRIAL PROCEDURES

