As mentioned earlier, blood and bone marrow cultures are the gold standard for diagnosis of typhoid. Alternatives diagnostic tests that are easier to use, faster and cheaper are required. Numerous alternative tests have been developed such as RDTs or PCR and are currently available in the market. However data on their performance are limited mainly because evaluation studies are commonly focusing on three tests (Tubex, Typhidot and Test-It). When an alternative test is evaluated, comparison of its performance to other tests may not be possible since the reference tests used may differ between studies: while blood and bone marrow cultures are the gold standards, the poorly performant Widal test is sometimes used as the reference standard. This lack of harmonization in the study protocols negatively impact the identification of promising typhoid diagnostic tests and the generalization of performance data in different geographical areas of the world. In addition, access to samples from typhoid patients clearly hampers the evaluation of new typhoid tests.

This collaborative study between KEMRI and FIND will systematically compare different point of care typhoid tests currently available in the market against the same set of reference standard in two geographically distant typhoid endemic areas in different continents (Asia and Africa). The knowledge gained from this trial may benefit health providers' by providing information on diagnostic accuracy of current typhoid test and to decide on utility of these commercial tests. The result obtained from this trial will also be made available to help inform the WHO Essential Diagnostic list (EDL) and stakeholder decision making more broadly.

As a part of the study a biorepository will be established at site with well characterized samples which can be used in future evaluations of emerging technologies and/or to support innovative test development.

WASTE MANAGEMENT AND BIOSAFETY OF THE STUDY

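### Outcome 2.1 gives one invalid or indeterminate percentage per RDT over a tested set that is half culture-positive by design; the rates should be reported by culture status

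*Combined protocol and SAP*

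**What the plan says.** The Secondary Endpoints section defines endpoint 2.1 as "Estimates of operational characteristics of different RDTs based on quantitative assessment including invalid and indeterminate rates". It names no population to which the rates should apply. Under Analysis of the secondary outcome(s), Outcome 2.1, the numbers of indeterminate and invalid results are given per RDT "together with the relative percentage over the total number of tests performed". No split by culture result, weighting or interval is specified.

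The tested set is selected on culture result. Under Study Design, "investigational RDTs will be performed on all blood culture positive and equal culture of negative serum". Under Study workflow, it is expected that "at least 100 blood culture positive and 100 blood culture negative samples will be tested with index tests". The Sample Size section says "The reported values for prevalence of Salmonella Typhi positive patients in Kenya is 5" per cent, and derives an enrolment of at least 2,000 from that figure.

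Two other parts of the Statistical Analysis Plan section bear on this. Estimates of accuracy removes missing and invalid results from the analysis without imputation. Baseline descriptive statistics plans a breakdown by reference result, but for the included samples, not for the invalid or indeterminate results of each test.

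**The concern.** Sensitivity and specificity are each calculated within one culture group, so testing positives and negatives in equal numbers does not distort them. A percentage over all tests performed is not calculated within a group. Its value depends on the ratio in which the groups were sampled whenever the two groups have different rates.

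Two things are at stake. First, Expected Application of the Results says that the findings should help health providers "to decide on utility of these commercial tests". A provider sees suspected cases, of whom about one in twenty is expected to be culture-positive, and may read the reported rate as applying to that mix. Second, invalid results are removed before accuracy is estimated, so Outcome 2.1 is where a reader learns how many results each test lost. A single percentage does not show which accuracy estimate lost them.

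**Working it through.** **Inputs from the documents.** Enrolment 2,000 and culture positivity 5% (Sample Size); 100 positive and 100 negative sera tested (Study workflow); Outcome 2.1 denominator, all tests performed.

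**The plan's own figures.** Enrolment: 100 / 0.05 = 2,000. Stated precision: (1.960 + 0.842) × √(0.5 × 0.5 / 100) = 0.140, the planned ±14%. Both reproduce, and this point does not affect them.

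**Mix of the two sets.**
- Tested: 100 / (100 + 100) = 50% culture-positive.
- Enrolled: 100 / 2,000 = 5% culture-positive.
- Sampling fractions: 1 for positives; 100 / 1,900 = 0.053 for negatives.

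**Formulas,** counting one test per serum:
- Pooled rate, as planned: 0.50 × r1 + 0.50 × r0.
- Enrolled-mix rate: 0.05 × r1 + 0.95 × r0.
- Difference: 0.45 × (r1 − r0).

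**Illustration.** The documents give no r1 or r0, so the values below are assumed.

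| r1 | r0 | Pooled | Enrolled mix | Difference (points) |
|---|---|---|---|---|
| 2% | 2% | 2.0% | 2.0% | 0 |
| 4% | 2% | 3.0% | 2.1% | +0.9 |
| 6% | 2% | 4.0% | 2.2% | +1.8 |
| 10% | 2% | 6.0% | 2.4% | +3.6 |
| 2% | 10% | 6.0% | 9.6% | −3.6 |

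For scale, the standard error of the pooled rate at (4%, 2%) is 0.5 × √(0.04 × 0.96/100 + 0.02 × 0.98/100) = 1.2 points, more than the 0.9-point difference. For 12 of 200 (6.0%) the Wilson 95% interval is 3.5% to 10.2%, which excludes 2.4% but not 9.6%.

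**What the single figure hides.** The last two rows both report 6.0%, or 12 results of 200. If all 12 are invalid and each test is taken alone, the first case leaves 90 sera for sensitivity and 98 for specificity; the second leaves 98 and 90. Split by culture status, the Wilson intervals are 5.5% to 17.4% for 10/100 and 0.6% to 7.0% for 2/100.

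**Ranking.** A reversal can be constructed. Test A at (10%, 2%) and test B at (4%, 4%) give 6.0% and 4.0% pooled, but 2.4% and 4.0% in the enrolled mix. In a simulation with 100 sera per group and independent tests, A came out worse than B in 79% of runs on the pooled rate and in 26% on the weighted rate.

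**Precision of weighting.** At a common rate of 3%, the pooled standard error is √(0.03 × 0.97 / 200) = 1.2 points. The weighted one is √((0.05² + 0.95²) × 0.03 × 0.97 / 100) = 1.6 points.

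**The case against.** The plan states its denominator openly and nowhere presents Outcome 2.1 as a rate among suspected patients. The enrolled-mix rate is a different target, so the 0.45 × (r1 − r0) difference is an error only for a reader who wants that target. This stands. A reader might infer that the plan reports a biased clinic rate, but no such rate is claimed.

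The documents also give no reason why a failed test should depend on culture status. Borderline readings might plausibly follow antibody or antigen level, but that is an outside argument, and the RDT case report form offers only positive, negative and invalid. If r1 = r0, the difference vanishes. This stands as a limit on size. It does not justify assuming equality, and the planned figure would not reveal a difference.

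The enrolled-mix rate has weaknesses of its own. The plan does not say how the tested negatives are chosen, so weighting assumes that they represent all enrolled negatives. The tests are also run in monthly batches by trained laboratory staff, so even a weighted rate is not a point-of-care failure rate. Both stand, and they are why weighting should only supplement the rates by culture status.

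Finally, the section calls itself a summary, leaves detail to a later SAP, and already plans a breakdown by reference result. That breakdown covers included samples only, and the Outcome 2.1 denominator is already fixed in the text, so this answers the point only in part.

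**Conclusion.** The point holds as a minor one. The planned percentage depends on the 1:1 sampling ratio if the rates differ by culture status, and it cannot show which accuracy estimate loses the removed results. The second limitation applies whatever target population is chosen.

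The size rests on assumed rates, 100 sera per culture group and 5% positivity: no difference if r1 = r0, 0.9 points for a 2-point gap and 3.6 points for an 8-point gap. At 10% positivity the multiplier would be 0.50 − 0.10 = 0.40.

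Two stronger readings are not supported. A reader might conclude that Outcome 2.1 will misorder the tests; that needs large gaps that differ between tests, and the documents report none. A reader might also take the 50% and 5% as shares with typhoid. They are culture-positive shares, and the Justification for the Study says that culture can miss typhoid. Nor does the text say that invalid and indeterminate counts are merged into one rate; the pooling meant here is across culture groups.

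**What to change.** Amend the Outcome 2.1 rule in the SAP as follows.

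- For each RDT, report the number and percentage of invalid and, separately, of indeterminate results in culture-positive and in culture-negative sera, with Wilson 95% intervals. Label any pooled figure as a 1:1 culture-status mix.
- As a supplement, give the two rates weighted by the culture-positive and culture-negative shares among enrolled participants with a culture result. Use an interval suited to a weighted sum of two proportions, for example one that combines the two Wilson intervals, because a single-proportion Wilson interval does not apply. State that the figure assumes the tested negatives represent all enrolled negatives.
- Define what counts as a test performed. The RDT form has repeat lines for invalid results and separate IgG and IgM lines for several tests. Ten initial invalids give 10/200 = 5.0%, or 10/210 = 4.8% if ten valid repeats enter the denominator.
- Add an indeterminate option to the RDT form. This is needed whether or not the rates are split, because endpoint 2.1 names a rate that the form cannot record.

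The cost is a short SAP edit and one form option. Culture results are already collected, so splitting the invalid rates needs no new data. The weighted rate is less precise (standard error about 1.6 against 1.2 points at a common 3% rate), and each rate by culture status rests on about 100 sera.
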